## 5.6.b. Data Analysis

**Power and Sample Size Calculations.** This study is powered on weight change at six months, comparing intervention and control conditions. We used formulas specified by Friedman et al. for use in clustered randomized controlled designs. Sample size was calculated for continuous outcomes and inflated to account for clustered randomization, using the inflation factor  $1 + (m - 1)\rho$  for cluster size  $m$  and intraclass correlation  $\rho$ , and attrition. Based on outcomes in prior weight loss trials, **we expect those in *MOVE!+UP* to lose 12 pounds on average, which would likely correspond to clinically meaningful weight loss (5% of baseline weight).** The specified expected weight loss is plausible, given *MOVE!+UP* pilot participants lost an average of 14 pounds, corresponding to 6% of baseline weight. We expect those in the control condition to achieve weight loss of 3.6 pounds on average consistent with Veterans with PTSD who participate in *MOVE!*, according to administrative data.

In the power calculation, the standard deviation of the outcome was assumed to be 13 based on previous findings. We calculated this value based on the marginal SD of 50 for baseline weight observed among Veterans with PTSD in *MOVE!*, between baseline and 6-month weight observed in the *MOVE!+UP* pilot (comparable to other weight loss effectiveness trials). Comparing these outcomes, an 8.4 pound difference in weight lost corresponds to prior behavioral weight loss trials and would yield a medium Cohen's  $d$  effect size of 0.65.

Table 7 displays the sample size required for varying cluster sizes *m* and intraclass correlation coefficients  $\rho$  assuming 90% power. The sample size of N=164 total Veterans (82 Veterans per treatment arm) chosen for this study assumes an ICC of 0.03, cluster size of 8 Veterans per randomized group, 90% power, a two-sided  $\alpha$  of 0.05, and a 6-month attrition rate of 25%, similar to MOVE!+UP pilot’s overall retention and a meta-analysis of missing data in weight loss RCTs. We will also be powered to detect a meaningful change in PTSD symptoms in the intervention condition at six months, aligned with the average PTSD symptom reduction of 18 (SD=12) observed among MOVE!+UP pilot cohort 5 participants and assuming a 9-point clinically meaningful reduction in the control condition.

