### Statistical Analysis—Specific Aim 1 Primary Outcome.

We will test the primary hypothesis that among Veterans with overweight or obesity, MOVE!+UP will result in significantly greater weight loss using linear mixed effects models. Because this is an RCT, no imbalance across conditions is anticipated. To increase precision of outcome effect estimates, the analysis will adjust for baseline weight and an indicator of self-reported African-American status. Participants in the same enrollment cohort who are assigned to the same treatment arm receive group treatments together, so their outcomes are correlated. To account for this, we will include a random intercept for group treatment cluster in the model. The primary analysis will be based on the following model:

$$Y_{ij}^{(6)} - Y_{ij}^{(0)} = \beta_0 + \beta_1 Intervention_i + \beta_2 Y_{ij}^{(0)} + \beta_4 x_i + \tau_j + \varepsilon_{ij}$$

Where:

- $Y_{ij}^{(6)} - Y_{ij}^{(0)}$  is the *difference in weight at 6 months* ( $Y_{ij}^{(6)}$ ) and baseline ( $Y_{ij}^{(0)}$ ) for subject  $i$  in group treatment cluster  $j$ ;
- $Intervention_i$  is an indicator of assignment to the intervention MOVE!+UP;
- $Y_{ij}^{(0)}$  is baseline weight;
- $x_i$  are baseline covariates; and
- $\tau_j$  is the random intercept for group treatment cluster  $j$ .

Our main goal is to test whether  $\beta_1=0$ , which is the difference in weight change between intervention and control groups. A strength of our approach includes accounting for correlated responses among intervention participants in the same treatment cluster. The approach we chose assumes a homogenous variance between the clusters (cohorts); a recent study showed this may be acceptable in scenarios where ICCs are low, as assumed in our study. Our approach of adjusting for baseline weight and pre-specified baseline covariates will provide the most efficient way of estimating the effect of intervention.

We will calculate a point estimate and 95% confidence interval for the effect of intervention,  $\beta_1$ , based on the fitted mixed effects model. A test of the null hypothesis of no intervention effect,  $\beta_1=0$ , will be conducted using a significance threshold of 0.05. The test will be based on a t-statistic with denominator degrees of freedom calculated using the Kenward-Rogers approximation. Since we are only testing a single hypothesis for the primary analysis, no adjustment for multiplicity will be needed.

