**Note: Aim 3 analyses are not covered in this statistical analysis plan.**

Table 1. Statistical Models

Analysis	Outcome(s)	Independent Variables
Primary analysis	6-month absolute weight change from baseline (pounds)	Binary treatment indicator  Baseline weight  Binary African-American race indicator
Secondary analyses	1. 6-month absolute change in PTSD symptoms from baseline 2. 12-month absolute change in PTSD symptoms from baseline 3. 12-month absolute weight change from baseline (pounds)	Binary treatment indicator  Baseline outcome  Binary African-American indicator (weight analysis only)
Exploratory analyses	6-month absolute change from baseline in: 
 
Diet quality
 
Eating habits
 
Night eating
 
Emotional eating
 
Average MVPA and average LMVPA (adjust for total # of valid days at baseline and 6 months)
 
Social support – Diet
 
Social discouragement – Diet
 
Social support – physical activity
 
Social discouragement – physical activity
 
Insomnia Severity Index (ISI)
 
Depression symptoms
 
Internalized Weight Bias
 
	Binary treatment indicator  Baseline outcome

 All models account for clustering through the inclusion of a random intercept for group treatment cluster.

Analysis	Outcome(s)	Independent Variables
Exploratory Analyses	Binge eating at 6 months	Binary treatment indicator
Sensitivity analyses:  adjusting for prior weight loss treatment	1. 6-month absolute weight change from baseline (pounds) 2. 12-month absolute weight change from baseline (pounds)	Binary treatment indicator  Baseline outcome  Binary African-American indicator  Total number of MOVE! visits 12 months prior to baseline  Binary indicator of prescription weight loss medications at baseline
Sensitivity analyses:  adjusting for prior mental health treatment	1. 6-month absolute change in PTSD symptoms from baseline 2. 12-month absolute change in PTSD symptoms from baseline	Binary treatment indicator  Baseline outcome  Total number of mental health visits 12 months prior to baseline, per EHR  Number of PTSD visits in the prior year  Binary indicator of PTSD medications in the last year

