Sensitivity analyses:  Including auxiliary variables to assess impact of missing data	1. 6-month absolute weight change from baseline (pounds) 2.	Binary treatment indicator  Baseline outcome  Binary African-American indicator (weight analyses only)  Auxiliary variables discussed in the Handling of Missing Data section. Plus those that appeared possibly associated with missingness on 6-month weight in descriptive comparisons.
Sensitivity: bariatric surgery	1. 6-month absolute weight change from baseline (pounds) 2. 12-month absolute weight change	Binary treatment indicator

Analysis	Outcome(s)	Independent Variables
influence	from baseline (pounds)	
Baseline outcome
 
Binary African-American indicator (weight analyses only)
 
Remove veteran outcome with bariatric surgery. However no one had bariatric surgery during the study period so this analysis is not being conducted.

Sensitivity analysis: examine differences in utilization across tx conditions and the influence of these factors on weight loss outcome.	
 
1. 6-month absolute weight change from baseline (pounds)
 
2. 12-month absolute weight change from baseline (pounds)
 
3.
 
	
Binary treatment indicator
 
Baseline outcome
 
Binary African-American indicator (weight analyses only)
 
-Binary indicator of prescription weight loss medications from baseline to 6 and 12 months reported in EHR and/or self report
 
-binary indicator of non-MOVE! +UP/MOVE! weight management care (i.e., any self-reported non-Va program, dietician visits TeleMOVE!). Will not include self-reported use of websites, Fitbits etc.
 
If the pattern of results changes from what was found in the primary analysis, we would pursue a formal mediation analysis.

Sensitivity analysis: If we see substantial issues with the q-q plots when the primary analysis is	
 
1. 6-month log-transformed weight change from baseline (pounds)
 
1.
 
	
Binary treatment indicator
 
Baseline outcome
 
Binary African-American indicator (weight analyses only)

Analysis	Outcome(s)	Independent Variables
run, we will do a sensitivity analysis with a log-transformed outcome		

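### The fallback analysis for a poor q-q plot takes the log of weight change in pounds, which does not exist for anyone who lost weight

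*Combined protocol and SAP*

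**What the plan says.** Section 5.6.b, under the Aim 1 primary outcome, defines the dependent variable by an equation: weight at 6 months minus weight at baseline, described as the "difference in weight at 6 months" and baseline. Weight loss is therefore negative. Table 1 (Statistical Models) lists the same outcome as "6-month absolute weight change from baseline (pounds)". The equation fixes the meaning of the word absolute there: a signed change in pounds, not a percentage and not a magnitude without sign.

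The last row of that table is conditional. It begins "If we see substantial issues with the q-q plots when the primary analysis is" run, and continues "we will do a sensitivity analysis with a log-transformed outcome". Its outcome cell reads "6-month log-transformed weight change from baseline (pounds)", and its covariates are the treatment indicator, the baseline outcome and the African-American indicator. The plan gives no offset, sign reversal, ratio, or rule for zero or negative values.

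The power section of 5.6.b supplies the expected values: "we expect those in *MOVE!+UP* to lose 12 pounds on average", a mean loss of 3.6 lb in control, and an SD of 13 lb for weight change.

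**The concern.** A log transform needs positive values. In a weight-loss trial the expected change is negative in both arms, so the transform fails for the typical participant. This row is the only response that the plan states to non-normal residuals in the primary model. It would be called on only when the normality assumption behind the primary inference is in doubt, and in that situation the plan would offer no check that can be run.

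Two things could follow. The analysis could be abandoned or repaired after the data are seen, for example by adding a constant whose size the analyst chooses. Or it could be run on the records where the log exists. That subset would be selected on the outcome, at a different rate in each arm, which does not fit the intent-to-treat commitment in the same section. Multiple imputation does not avoid the problem, because imputed 6-month weights also produce negative changes.

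**Working it through.** **Inputs, all from section 5.6.b.** Mean change −12 lb (MOVE!+UP) and −3.6 lb (control); SD of change 13 lb; 82 per arm; cluster size 8; ICC 0.03; attrition 25%; two-sided alpha 0.05; power 90%. The normal shape is an assumption of this check.

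**1. Reproduce the plan's own figure.** This confirms that these are the values the plan used.
- Per arm before inflation: 2 × (13 × (1.960 + 1.282) / 8.4)² = 50.33.
- Design effect: 1 + (8 − 1) × 0.03 = 1.21.
- After attrition: 50.33 × 1.21 / 0.75 = 81.2, rounded up to 82 per arm, 164 in total. This matches the plan. The same formula gives all six rows of Table 7 (196, 182, 172, 164, 148, 144).

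**2. Share of participants for whom the log is undefined.** P(change < 0) = Φ(mean loss / SD).
- MOVE!+UP: Φ(12/13) = 0.822, about 67 of 82.
- Control: Φ(3.6/13) = 0.609, about 50 of 82.
- Both arms together: (0.822 + 0.609) / 2 = 0.716.

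Counts are before attrition. A change of exactly zero is also undefined and would add to them.

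**3. Range over the SD.**

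| SD (lb) | MOVE!+UP undefined | Control undefined |
|---|---|---|
| 10 | 88% | 64% |
| 12.25 | 84% | 62% |
| 13 | 82% | 61% |
| 16 | 77% | 59% |

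The SD of 12.25 is the one implied by the plan's baseline SD of 50 and within-person correlation of 0.97: 50 × √(2 × 0.03) = 12.25.

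**4. Who would remain.** Only people who gained weight: 1 − 0.822 = 17.8% of MOVE!+UP (about 15 of 82) and 1 − 0.609 = 39.1% of control (about 32 of 82). The retention rates differ by 21 percentage points. The mean change among gainers is μ + SD × φ(a) / (1 − Φ(a)), with a = −μ/SD:
- MOVE!+UP: −12 + 13 × 0.2605 / 0.1780 = 7.0 lb.
- Control: −3.6 + 13 × 0.3839 / 0.3909 = 9.2 lb.
- Difference: −2.1 lb, against −8.4 lb in the full population. These are pound-scale means, given to show the selection. They are not what a log-scale model would estimate.

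**5. Would log weight cure the q-q problem?** Log(6-month weight) is always defined, but 6-month weight ratios lie near 1. A 12 lb loss that equals 5% of baseline implies a baseline of 12 / 0.05 = 240 lb and a ratio of 0.95, where the log is almost linear. In a simulation with assumed baseline mean 220 to 260 lb, SD 50, weights held to 150–440 lb, and change SD 13:
- Residual skewness of −1.0 in pounds became about −1.4 on the log scale, which is worse.
- Residual skewness of +1.0 fell only to about +0.8.

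**The case against.** The strongest reply is that the authors meant change in log weight, log(Y6) − log(Y0), which is defined for everyone. The row gives this some support: it adjusts for the baseline outcome, and a change score has no baseline value, so outcome in that cell must mean weight. The table is also unpolished, with stray empty list numbers. But the outcome cell names weight change and gives pounds as the unit, and a log ratio has no pounds. The reading is possible, not established. If it was intended, the row still needs rewording.

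A second reply is that a log of negative numbers in roughly 70% of records would be obvious to the study biostatisticians. That is fair. A reader might infer that the analysis would silently discard participants and then be reported as failing to confirm the primary result. The documents do not support that: they contain no rule for dropping undefined values, and they attach no decision to this row.

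A reader might also infer that reversing the sign, to the log of pounds lost, is the planned analysis, and that it would shrink the effect from 8.4 to about 4.3 lb. It would indeed lose 18% of MOVE!+UP and 39% of control. But the plan states no sign reversal, and 4.3 lb is a pound-scale figure that a log analysis would not estimate.

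Finally, the percentages assume normality while the row is triggered by non-normality. This limits their precision. It does not change the conclusion, because a single participant who loses weight makes the transform undefined.

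**Conclusion.** The point holds, within limits. As written, the fallback analysis cannot be run. At the plan's means and SD of 13 lb the log is undefined for about 82% of MOVE!+UP and 61% of control, and for a majority of both arms across SDs of 10 to 16 lb. The exact shares rest on the planning means and an assumed normal shape; the failure itself rests only on some participants losing weight. Any version confined to defined values would analyse weight gainers alone, selected on the outcome at different rates by arm.

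This is a defect in one conditional sensitivity analysis. The primary mixed model, its test and interval, the sample size, the imputation plan and the other sensitivity analyses are unaffected. It would be wrong to read it as a threat to the primary result.

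**What to change.** Replace the row with the primary pound-scale model, same covariates and random intercept, and take the confidence interval and p-value from a bootstrap or permutation procedure that respects the treatment clusters. This answers the non-normality that triggers the row and keeps everyone in the analysis. State in advance the resampling unit and how the procedure combines with the 50 imputed datasets.

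If a log-scale check is still wanted, specify log(6-month weight) as the outcome, adjusted for log(baseline weight) with the same covariates and random intercept. It is defined for everyone and gives a ratio of 6-month weights. It should not be the only remedy, since it does little for residual shape.

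The cost is the wording of one table row and a little more computation. No new data are needed.

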## 5.8 Union Notification

Of note, during the pilot, we notified the union of our research and recruitment of VA employees (Aim 3) for the purposes of that (essentially identical) study, and the Union Representative reviewed our interview guide and determined that as our study does not concern employees' conditions of employment, union notification is not required (see submitted Union Approval).

Regarding our Veteran participants (Aim 1 and 2), we likely won't know if a Veteran is also an employee until we open up their medical chart in CPRS. However, we confirmed eligibility (diagnoses and participation in care) in the Veteran's medical record in CPRS during the recruitment and screening process. Furthermore, because study participation may involve weekly intervention sessions, any Veteran employees who might be interested in participating would also need to participate on their own time (that is, during their off hours), so we would likely be able to ascertain if an interested participant is also a Veteran employee fairly early on. Regardless, because we do not explicitly discuss conditions of Veteran employees' employment in any of our questionnaires or interviews, we felt we did not need to pursue union notification/approval as we do not meet that criteria (given to us by the union representative as noted above) for union review.

## 6.0 Reporting

**Safety Assessment.** Opportunities for participants to systematically report safety data occurred during the baseline assessment visit, 6-month assessment visit, and the 12-month assessment visit (see attached Medical History AE Assessment). Specifically, study staff administered a medical history AE assessment at the 6- and 12-month visits. Safety information also was collected when reported in clinical or other encounters with members of the study team (e.g., interventionists, MOVE! clinicians, and/or research staff). [name] and [name] (DSMC

member) independently assessed each AE reported on the Medical History AE form or to study team members for expectedness in the study population, severity, start and resolution times and relation to study activity. They also w identified any important follow-up activities to ensure appropriate care is received. With respect to actions that need to be taken on SAEs, [name] in consultation with the DSMC, would make recommendations regarding the following: consideration of early termination of the study due to treatment safety concerns, and modification of the study protocol regarding areas of recruitment, participant retention, outcome assessment, statistical analysis, or general trial operations. For AEs reported during the intervention phase, they were monitored on at least a weekly basis until deemed to have been resolved. If they were ongoing after the 16-session intervention phase, they were reassessed on a weekly basis for participants whose care team wass not yet engaged; once the care team is engaged in managing the issue, the AE wouldl only be reassessed at the 6-month (and 12-month if needed) assessment timeframe until it is resolved. No assessment of AEs will continue beyond the 12-month assessment timeframe unless deemed necessary by the DSMC.

Development or exacerbation of the following conditions or states are expected AEs in participants who have a high BMI and PTSD and adopt healthy eating and physical activity program:

- Gastrointestinal symptoms related to diet;
- Musculoskeletal symptoms or injury resulting from physical activity;
- Weight associated disorders including diabetes, hypertension, liver disease, cardiovascular disease, asthma, COPD, clotting problems, and other lung related conditions;
- Other conditions associated with unhealthy health behaviors, such as from tobacco and alcohol disorders (e.g. cancer);
- Age-related illnesses;
- Mental health symptom exacerbations;
- COVID-19 (SARS-CoV-2) infection due to population prevalence;
- Unhealthy eating behaviors (e.g., binge eating)

Study progress and safety are reviewed in weekly staff meetings (and more frequently if needed). The frequency and type of data review for this study differs according to the type of data and can be summarized in Table 8 below.

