### 2. Research Design:

Using a hybrid type 1 trial framework, 179 overweight/obese Veterans with PTSD enrolled in PTSD care enrolled in the study and n=174 were randomized to either usual care enhanced with enrollment in MOVE! (control) or usual care enhanced with MOVE!+UP (intervention). This study is guided by three aims: 1) Test whether intervention participants have greater 6-month weight loss (primary outcome) and 6-month PTSD symptom reduction and 12-month weight loss and PTSD symptom reduction (secondary outcomes), relative to controls; 2) Assess whether compared to control, intervention participants have greater improvements on 6-month treatment targets: physical activity, eating behavior, insomnia, depression, and social support; 3) Estimate intervention and control condition costs and utilization, and identify MOVE!+UP implementation barriers and facilitators, to contextualize Aim 1 and inform future implementation.

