### 5.3 Informed Consent Procedures

Consent was obtained by a trained research staff member who meets all facility education requirements in the protection of human research subjects or by one of the study investigators. Study staff received thorough training on informed consent procedures from the study PI. The Oral Scripts that document verbal consent has been obtained for

participation were sent to the RCO using standard compliance procedures (encrypted email).

a. Veteran participants (Aims 1 and 2)

Study staff contact Veterans by telephone to assess eligibility and interest. For those eligible based on screening criteria, a follow-up virtual eligibility confirmation and enrollment visit, held over phone or VVC (or other approved video conferencing modality should VVC not be working), was scheduled. The Information Statement was mailed to the Veteran and was reviewed over the phone or VVC using our Oral Script that includes a protocol and space for obtaining staff signature to confirm verbal consent was provided. Staff ensured that participants were given an opportunity to ask questions about all aspects of the study, and that they understood what study participation will involve. Potential participants were informed that their decision regarding participation will in no way affect the services they receive, and that they may decline to answer any questions or decline any services offered as part of the project. Declining any one service would not affect their ability to receive other services from the project. They also were informed that this study is a randomized trial and that they had an equal chance of receiving MOVE! or MOVE!+UP. Veterans also provided verbal consent for Use of Picture and/or Voice during the screening process. Study staff also documented whether or not they provided verbal consent to participate over the phone or by VVC.

Staff also used this time to discuss the Group VVC Telehealth consent agreement, which details the use of VVC to deliver the MOVE! and MOVE!+UP group sessions (see ALT Group VVC Telehealth Agreement).

b. VA Employees (Aim 3)

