4. *For all participants:* We will capture CDW/CPRS administrative utilization data from 12 months prior to baseline through 12 months post-baseline, including *MOVE!* visits, dietitian visits, primary care, mental health group and individual psychotherapy, and psychiatry care. We also will assess prescription of psychiatric and obesogenic and leptogenic medication from VA pharmacy files. Outpatient utilization will be drawn from administrative data, classified using an algorithm developed by a study team including Co-I [name] that defines groupings of CPT codes and provider specialty codes. Inpatient care will include all cause, psychiatric, and ambulatory care-sensitive condition hospitalizations, as identified in prior studies. We also

will pull bariatric surgery from the EHR from baseline through 12 months post-enrollment to be included in a previously planned sensitivity analysis.

If the trial is positive, costs for encounters in these categories will be measured using the VA Managerial Cost Accounting (MCA) system, adjusted for inflation. We also will capture # of Veterans eligible, ineligible, contacted, recruited and retained, and psychiatric and medical conditions associated visits in the year prior to and 12 months following enrollment (pulled through administrative data).

Starting with cohort 4, we informed participants at enrollment into the study that administrative data will be pulled even if they cease participation in the study, to ensure we have sufficient power to conduct exploratory analyses examining these administrative data-based outcomes, while introducing no additional burden to study participants.

For participants from cohorts 1-3 who withdrew from the study, administrative data will be pulled up through the date of withdrawal. However, participants from cohort 2 and 3 were asked whether they were willing to allow us to pull data from the medical record through 15 months using our phone script. We documented their response in a NTF, submit it to the IRB, and document their decision in our database.

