If a participant decided to withdraw, or if they were terminated from the study, a person from the study team may need to meet with them to discuss the necessary steps that they may need to take to end Veteran participation in the study. Veterans were also reminded that If they decided to withdraw from the study, no new information would be collected from them (aside from prospective CDW data, noted in the consent as described above); however, data already collected will continue to be part of the analyses.

b. VA Employees (Aim 3)

VA staff participants will be assured that they can, at any time, refuse to answer any question, and at any time elect to withdraw from the study. They also will be assured that their participation or lack thereof will not be reported to their supervisor or peers nor will it have any impact on their work environment and that they are free to participate in the presence of union representation.

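### Serious adverse events are found only through visits and reports to staff, and the planned VA hospitalisation extract is not linked to safety review, so events among non-attenders and withdrawals may be under-counted

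*Combined protocol and SAP*

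**What the plan says.** Section 6.0 (Safety Assessment) says that "study staff administered a medical history AE assessment at the 6- and 12-month visits". It adds that safety information was taken when reported in clinical or other encounters with the study team, naming interventionists, MOVE! clinicians and research staff. The two raters assess what comes in on the form or is told to the team. Neither that section nor the DSMC text after it describes a search of charts or administrative data for serious events, and SAE reporting starts once staff discover one.

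Section 5.5 (Manually tracked and administrative data) plans a VA utilisation extract from 12 months before to 12 months after baseline, under an item headed as applying to all participants: "Inpatient care will include all cause, psychiatric, and ambulatory care-sensitive condition hospitalizations". Its stated purpose is Aim 3, which the analysis plan says it does not cover. From cohort 4, participants were told that "administrative data will be pulled even if they cease participation in the study". For withdrawals in cohorts 1 to 3 the data stop at the withdrawal date, although cohort 2 and 3 participants were asked whether they would allow a longer pull.

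Section 5.7 tells Veterans: "If they decided to withdraw from the study, no new information would be collected from them". It excepts prospective administrative data. Section 5.6.b plans on "a 6-month attrition rate of 25" per cent.

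**The concern.** A participant who stops attending and stops talking to staff can be admitted to a VA hospital without the admission ever being rated as a serious event. The same admission would still appear in the Aim 3 utilisation data. A formal withdrawal loses both safety routes, because only administrative data continue, and those do not feed the event log.

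The loss may be informative. Section 6.0 lists mental health exacerbation and cardiovascular disease among the events expected in this population. Either can lead to admission, and either could make someone stop attending. Section 5.7 also says the study would likely withdraw a participant who expressed suicidal intent or had an extreme PTSD exacerbation attributed to participation. The trigger would be known to the team, but a later psychiatric admission might not be.

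Capture may differ by arm. Section 5.6.a has MOVE!+UP facilitators exchanging weekly weights and PTSD symptom assessments with participants. For controls, Section 5.5 describes reminders to promote attendance at initial MOVE! sessions, though MOVE! clinicians are a named reporting route. The direction of any difference cannot be told from the documents. At stake are the completeness of the final SAE count and its consistency with the trial's own utilisation data.

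**Working it through.** **Inputs from the documents.** Planned sample 164, "82 Veterans per treatment arm"; 6-month attrition 25%; difference 8.4 lb; SD 13 lb; ICC 0.03; cluster size 8; two-sided alpha 0.05; power 90% (all Section 5.6.b). Actual size: "n=174 were randomized" (Abstract, Research Design). The documents give no SAE rate, no count of withdrawals and no 12-month attrition figure.

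**Reproducing the plan's figure.** Per arm before inflation: 2 × (13 × (1.960 + 1.282) / 8.4)² = 50.33, using unrounded quantiles. Design effect: 1 + (8 − 1) × 0.03 = 1.21. With attrition: 50.33 × 1.21 / 0.75 = 81.2, rounded up to 82 per arm, or 164 in total. This matches, and the same steps give all six rows of Table 7. So 25% is the planning figure behind the sample size, correctly applied.

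**People without a 6-month form at that attrition.** 0.25 × 164 = 41. 0.25 × 174 = 43.5, about 44. These are upper figures for people with no safety contact, since a missed 6-month visit does not close the other routes.

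**Share of serious events missed.** Let d = 0.25 be the fraction not attending, k their risk relative to attenders, and s the fraction of their events that reach staff by another route. Then

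share missed = d·k·(1 − s) / ((1 − d) + d·k).

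| k (assumed) | s (assumed) | Calculation | Share missed |
|---|---|---|---|
| 1 | 0 | 0.25 / 1.00 | 25% |
| 1 | 0.5 | 0.125 / 1.00 | 12.5% |
| 2 | 0 | 0.50 / 1.25 | 40% |
| 2 | 0.5 | 0.25 / 1.25 | 20% |

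**Numbers of events.** If 2%, 5%, 10% or 20% of 44 non-attenders had a serious event in the unobserved time (assumed rates), the expected counts are 0.9, 2.2, 4.4 and 8.8. The chance of at least one, 1 − (1 − r)^44, is 59%, 90%, 99% and almost 100%.

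**What the extract could recover.** It would cover VA admissions for participants who did not withdraw, for withdrawals from cohort 4 onward, and for cohort 2 and 3 withdrawals who agreed to a longer pull. It would not cover time after withdrawal for cohort 1 or for cohort 2 and 3 participants who did not agree, nor admissions outside the VA. Without withdrawal counts by cohort, the number recovered cannot be computed.

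**The case against.** The strongest reply is that missing a visit is not the same as being lost. Non-attenders stay in intent-to-treat follow-up. They are pursued through a lost-to-follow-up protocol and alternate contacts (Sections 5.2 and 5.5), are phoned if the 16-week questionnaire does not come back, and are due a 12-month visit at which adverse events are recorded. This stands. A reader might infer that harms in a quarter of the sample are missed, but the documents do not support that: 25% is a planning assumption for 6-month attrition, and only formal withdrawals lose both routes.

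A reader might also infer that complete hospitalisation data on everyone are already in hand. They are not. The extract is written in the future tense, holds VA data only, and is cut at withdrawal for part of cohorts 1 to 3. Non-VA use is recorded at the 12-month visit, so it depends on attendance too.

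Nor do the documents show that the DSMC would routinely see the arm with more dropout as the safer one. Routine summaries to it are not split by arm, although it may ask for unblinded results, and it is consulted on significant data loss.

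Finally, the research risks are described as minimal, and the AE form and Safety Protocol are attachments not available here, which might call for chart checks. Neither point closes the gap in the protocol text, where the extract and the safety review are not connected.

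**Conclusion.** The point holds as a cheap improvement. As written, the SAE count depends on attendance and on contact with staff, while a planned source that depends less on either is left out of safety review. Serious events may be under-counted, most clearly after formal withdrawal and possibly unequally by arm. The missed share ranges from 12.5% to 40% across the scenarios shown, which rest on 25% attrition and on assumed relative risks and reporting fractions. The number of people concerned at 6 months is at most about 41 to 44 under that attrition. Sample size, power and alpha are unaffected.

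**What to change.** In Section 6.0, add one close-out reconciliation. After confirming with the IRB that safety use of the extract is covered, match the Section 5.5 inpatient data, from randomisation to 12 months, against the SAE log for all randomised participants, within the consent limits for cohorts 1 to 3. Have the two existing raters assess unmatched admissions, and send them to the DSMC and IRB under the existing rules. Report all-cause and psychiatric VA hospitalisations by randomised arm as a safety table. State with it that non-VA admissions are not covered, nor is time after withdrawal for cohort 1 and for cohort 2 and 3 participants who did not agree to a longer pull.

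The cost is some rating work and a higher reported SAE count. The reconciliation will not help expedited reporting: no recurring pull is described, and a retrospective extract cannot serve the 5-day rule in Section 6.0.
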